#### 1.7.2 Additional hypotheses

The following additional hypotheses will be tested for potential labelling claims, according to the step-down hierarchy procedure described in section 1.7.3 below:

| Endpoint                                 |                  | Hypotheses  |  |
|--|------------------|---|--|
| Pain Freedom at 2 hours                  | H 0 : | Proportion of attacks in the Rehaler group with PF2
= Proportion of attacks in the sham group with PF2     |  |
| (PF2)                                    | Ha:              | Proportion of attacks in the Rehaler group with PF2
≠ Proportion of attacks in the sham group with PF2     |  |
| Freedom from Most                        | H 0 : | Proportion of attacks in the Rehaler group with MBSF2
= Proportion of attacks in the sham group with MBSF2 |  |
| Bothersome Symptom at 2
hours (MBSF2) | Ha:              | Proportion of attacks in the Rehaler group with MBSF2
≠ Proportion of attacks in the sham group with MBSF2 |  |
| Sustained Pain Freedom at                | H₀:              | Proportion of attacks in the Rehaler group with SPF24
= Proportion of attacks in the sham group with SPF24 |  |
| 24 hours (SPF24)                         | Hª:              | Proportion of attacks in the Rehaler group with SPF24
≠ Proportion of attacks in the sham group with SPF24 |  |
| Headache Score at 2 hours                | H₀:              | Mean HS2 attack score in the Rehaler group
= Mean HS2 attack score in the sham group                       |  |
| (HS2)                                    | H₁:              | Mean HS2 attack score in the Rehaler group
≠ Mean HS2 attack score in the sham group                       |  |

|                                | H 0 : | Mean MBS2 attack score in the Rehaler group           |
|--------------------------------|------------------|---|
| Most Bothersome Symptom        |                  | = Mean MBS2 attack score in the sham group            |
| Score at 2 hours (MBS2)        | Ha:              | Mean MBS2 attack score in the Rehaler group           |
|                                |                  | ≠ Mean MBS2 attack score in the sham group            |
|                                |                  | Mean FDS2 attack score in the Rehaler group           |
| Functional Disability Score    | H₀:              | = Mean FDS2 attack score in the sham group            |
| at 2 hours (FDS2)              | H a : | Mean FDS2 attack score in the Rehaler group           |
|                                |                  | ≠ Mean FDS2 attack score in the sham group            |
| Use of rescue medication       | H 0 : | Proportion of attacks in the Rehaler group with Res24 |
| from the 2 hours time point    |                  | = Proportion of attacks in the sham group with Res24  |
| until 24 hours (Res24)         | H a : | Proportion of attacks in the Rehaler group with Res24 |
| ulitil 24 liburs (Res24)       |                  | ≠ Proportion of attacks in the sham group with Res24  |
|                                | H 0 : | Mean PS48 attack score in the Rehaler group           |
| Participant Satisfaction at 48 |                  | = Mean PS48 attack score in the sham group            |
| hours (PS48)                   | Ha:              | Mean PS48 attack score in the Rehaler group           |
|                                | па.              | ≠ Mean PS48 attack score in the sham group            |
|                                | H 0 : | Mean LSS2 attack score in the Rehaler group           |
| Light Sensitivity Score at 2   |                  | = Mean LSS2 attack score in the sham group            |
| hours (LSS2)                   | H a : | Mean LSS2 attack score in the Rehaler group           |
|                                |                  | ≠ Mean LSS2 attack score in the sham group            |
|                                | H 0 : | Mean NS2 attack score in the Rehaler group            |
| Nausea Score at 2 hours        |                  | = Mean NS2 attack score in the sham group             |
| (NS2)                          | Ha:              | Mean NS2 attack score in the Rehaler group            |
|                                |                  | ≠ Mean NS2 attack score in the sham group             |
|                                |                  | Mean SSS2 attack score in the Rehaler group           |
| Sound Sensitivity Score at 2   | H₀:              | = Mean SSS2 attack score in the sham group            |
| hours (SSS2)                   |                  | Mean SSS2 attack score in the Rehaler group           |
|                                | Ha:              | ≠ Mean SSS2 attack score in the sham group            |
|                                | H 0 : | Proportion of attacks in the Rehaler group with FR48  |
| Freedom from Relapse at 48     |                  | = Proportion of attacks in the sham group with FR48   |
|                                | ц.               | Proportion of attacks in the Rehaler group with FR48  |
| hours (FR48)                   |                  | Proportion of attacks in the Renaler group with FR48  |
| hours (FR48)                   | Hª:              | ≠ Proportion of attacks in the sham group with FR48   |

 Table 2: Secondary end point analysis sequence and hypotheses

#### 1.7.3 Hypothesis testing method

All primary and secondary performance end points will be reported and hypothesis tested comparing the active and the sham device. The statistical analyses will test a null hypothesis assuming no difference in treatment effect between the active and sham device.

The hypothesis testing of the primary and secondary endpoints will be performed by an independent biostatistician who will be blinded to which of the two study groups used the active device and which used the sham device.

When analysing the Primary and Secondary Endpoints listed in the study protocol, the fixedsequence step-down will be used for determining labelling claims of the product when marketed. This method starts by conducting a hypothesis test of the primary endpoint. If the hypothesis test for this endpoint is positive (i.e. the null hypothesis of equal effect of active and sham device was rejected), the following will result:

- 1. The endpoint will be considered eligible for including as a claim in the product labelling.
- 2. The first hypothesis on the list of additional hypotheses (See section 1.7.2 above) will be tested. If the null hypothesis is rejected, this process is repeated for the next hypothesis on the list, continuing until a hypothesis test is found to be negative, at which point the step-down process is stopped

The hypothesis testing of primary and secondary end points will be conducted using the methods listed in Table 3:

| Endpoint
type | Endpoint  | Hypothesis testing method  |
|------------------|---|--|
|                  | Absence of moderate or severe pain at 2 hours
(AMSP2)
Pain Freedom at 2 hours (PF2)   | Odds ratios and Pearson's χ  significance tests
(two-tailed), comparing active and sham
device. Threshold p value in interim analysis:
0.0052 (O'Brien-Fleming spending function)
Threshold p value in full data set analysis: 0.048 |
| Binary           | Freedom from Most Bothersome Symptom at 2
hours (MBSF2)
Sustained Pain Freedom at 24 hours (SPF24)
Use of rescue medication from the 2 hours'
time point until 24 hours (Res24)
Freedom from Relapse at 48 hours (FR48)  | Odds ratios and Pearson's $\chi^2$ significance tests (two-tailed), comparing active and sham device. Threshold p value: 0.05  |
| Categorical      | 
 
Headache Score at 2 hours (HS2)
 
Most Bothersome Symptom Score at 2 hours (MBS2)
 
Functional Disability Score at 2 hours (FDS2)
 
Participant Satisfaction at 48 hours (PS48)
 
Light Sensitivity Score at 2 hours (LSS2)
 
Nausea Score at 2 hours (NS2)
 
Sound Sensitivity Score at 2 hours (SSS2)
 
 | Ordinal logistic regression using the
proportional odds model with device type
(active or sham) as the exposure variable.
Threshold p value: 0.05   |

Table 3: Hypothesis testing for primary and secondary endpoints

The following Stage 2 exploratory endpoints will be compared to corresponding baseline values reported at Site Visit 1:

- How many times in the past month has the participant taken respectively a prescription acute migraine drug or an over-the-counter acute analgesic, with the intention to treat migraine.
- Proportion of patients who used an opioid drug to treat migraine the past month
- Proportion of patients who have been hospitalized for migraine in the past month

All hypothesis tests will be performed on the ITT data set of attacks. In the resulting data set each attack will constitute a data point and each patient will constitute a cluster including from one to three data points. The statistical analysis will take clustering into account by using the adjusted  $\chi^2$  statistic for clustered binary data developed by Donner and Banting (Donner and Banting, 1988) and validated by others (Gonen et al., 2001; Jung et al., 2001). This method negates the risk of type I errors that is incurred if clustering is disregarded. In the event that changes are made to the statistical analysis plan, these changes will be submitted for approval to the Competent Authorities.

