16.2 Sample Size and Statistical Power

The study's key secondary endpoint is Pain Freedom at 2 hours (PF2). Recognizing that this is the ideal outcome for migraine patients, the study has been designed with a moderately high statistical power (80%) for PF2. The estimated study size of 174 included participants has been determined on the basis of data from the pilot study and post-market data collected in Denmark, Sweden and Germany from 2018 to 2020, indicating that the PF2 rate will be 30% in the active device group and 12% in the sham group, that each patient will contribute data from two attacks while in Stage 1, and that the total percentage of included patients not yielding analyzable data will be 30%. These data were utilized in a sample size analysis, conducted by simulation and using the χ^2 significance test adjusted for clustered data. Under the given assumptions and including 174 patients, the estimated power for PF2 is 80%. Pilot study and post-market data indicated an AMSP2 rate of 61% in the study will result in 95% power for AMSP2. Therefore, the clinical investigation will randomize at minimum 174 participants.

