### 1.5 Power and sample size calculation

#### 1.5.1 Assumptions

The estimated study size of 200 to 240 included participants has been determined on the basis of data from the pilot study (Fuglsang et al., 2018) and post-market data collected in Denmark, Sweden and Germany from 2018 to 2020.

To estimate the sample size for this trial, it was assumed that 12% of subjects in the sham group and 30% of subjects in the active group would experience PF2. For AMSP2, a 26% response rate in the sham group and a 61% response rate in the active group was assumed.

The primary statistical test for this analysis will be a  $\chi^2$  significance test adjusted for clustered data (using the methods of Donner and Banting (Donner and Banting, 1988)) since subjects could contribute more than one migraine attack. The intraclass correlation coefficient (ICC) from preliminary data on this device was 0.486. This is a group-sequential design with one interim analysis, so the O'Brien Fleming Spending function will be used to set significant thresholds of 0.0052 at the interim analysis and 0.048 at the final analysis.

Power and sample sizes were estimated via simulation using the above parameters for a  $\chi^2$  significance test adjusted for clustered data. These simulations assumed a third of subjects would have one migraine attack during the course of the study, a third of subjects would have two study attacks, and a third of subjects would have three study attacks. In the interim analysis, a more refined method of estimating number of attacks per participant will be employed, using the observed attack frequencies from the interim data (cf. section 1.4). Additionally, it was expected that 22% of subjects would drop out of the trial and 10% of attacks would have missing data at the 2 hour time point, for a total of 32% of randomized subjects that would not provide data usable for the statistical analysis of the primary or secondary endpoint.

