# 1.8 Homogeneity Across Study Sites

The homogeneity of the treatment effect across study sites will be evaluated using a generalized linear mixed model where device used and site are fixed effects and each patient is a random effect (cluster). Homogeneity of the treatment effect between subjects in the United States and subjects outside the United States will also be evaluated using a generalized linear mixed model. If heterogeneity is detected, exploratory analyses will be conducted, which may include adjusting analyses for baseline characteristics that significantly differ across sites.

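### No clustered method is specified for the seven ordinal secondary endpoints; fitted as written, their tests run at about 7–14% type I error instead of 5%

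*SAP*

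**What the plan says.** SAP 1.7.3, Table 3, assigns HS2, MBS2, FDS2, PS48, LSS2, NS2 and SSS2 to ordinal logistic regression, a "proportional odds model with device type" as exposure, with "Threshold p value: 0.05". The row names no participant term, no GEE and no robust variance.

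The text under the table applies to all hypothesis tests. Each attack is a data point, and "each patient will constitute a cluster including from one to three data points". On the method it says: "The statistical analysis will take clustering into account by using the adjusted" chi-square, which it describes as a statistic for clustered binary data. It adds that this removes the type I error risk of ignoring clustering.

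SAP 1.7.1 gives the formula for that statistic, for a binary outcome only. SAP 1.8 does put a participant random effect in a model, but only for homogeneity across sites and regions. Protocol 16.4 names no method for these endpoints.

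The secondary tests run in a fixed order that decides labelling claims, "continuing until a hypothesis test is found to be negative". In SAP Table 2 the ordinal endpoints hold positions 4 to 6 and 8 to 11 of twelve. Res24 is seventh and FR48 is last.

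**The concern.** The adjusted chi-square divides each arm's Pearson component by a variance inflation factor. That repairs the binary rows of Table 3. It has no counterpart in a proportional-odds regression on a 4- or 5-level score, so these seven tests have a stated intention to handle clustering and no method that does it. The model actually named computes its standard error as if a participant's attacks were unrelated. With positive within-participant correlation that standard error is too small and the test rejects too often.

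A fixed sequence controls error only if each test holds its own level. Suppose the device relieves pain but does nothing for nausea or sound sensitivity. The earlier gates then open legitimately, and the later tests run at an inflated level. A false rejection at FDS2 also opens Res24 and what follows. An undefined method further leaves the choice between a clustered and an unclustered fit until the data are in hand.

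**Working it through.** **Inputs from the documents.** 68 evaluable participants per arm (SAP Table 1: 200 randomized, 136 after dropout). One, two or three study attacks in equal thirds (SAP 1.5.1). As an alternative, the protocol's assumption in 16.2 that "each patient will contribute data from two attacks while in Stage 1". On correlation, SAP 1.5.1 says: "The intraclass correlation coefficient (ICC) from preliminary data on this device was 0.486". It does not say which outcome that value came from, and no ordinal score has its own value. The correlation is therefore varied from 0.2 to 0.6 as an assumption.

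**The plan's own figures.** The SAP states no error rate for these tests beyond the 0.05 threshold. The nearest check on the inputs is the power in SAP Table 1 at N=200.

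- Design effect: D = 1 + ρ·Σm(m−1)/Σm = 1 + 0.486 × (0+2+6)/(1+2+3) = 1 + 0.486 × 8/6 = 1.648.
- Effective attacks per arm: 68 × 2 / 1.648 = 82.5.
- At alpha 0.048, AMSP2 power is 99.6–99.9% against the stated 99.1%.
- PF2 power is 81.1% by formula and 81.6–81.8% by beta-binomial simulation, against the stated 85.5%.

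The PF2 difference is unexplained, because the SAP does not say how correlated outcomes were generated. Nothing below depends on it.

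**Level by formula.** A test that ignores D has actual two-sided level 2[1 − Φ(1.96/√D)]. With two attacks each, D = 1 + ρ.

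| ρ | D, 1/2/3 mix | Level | D, two each | Level |
|---|---|---|---|---|
| 0.2 | 1.267 | 8.2% | 1.200 | 7.4% |
| 0.3 | 1.400 | 9.8% | 1.300 | 8.6% |
| 0.486 | 1.648 | 12.7% | 1.486 | 10.8% |
| 0.6 | 1.800 | 14.4% | 1.600 | 12.1% |

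**Level by simulation.** 8,000 null trials per scenario, using a latent-normal score with a participant effect. Assumed cumulative category probabilities are 0.20/0.45/0.75 (4-level) and 0.15/0.35/0.55/0.80 (5-level). The test is the proportional-odds score test, without and with variance taken from participant sums. Results for the 4-level score, 1/2/3 mix, 68 per arm:

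| Latent ρ | Unadjusted | Mean SE ratio, clustered/unadjusted |
|---|---|---|
| 0.2 | 8.0% | 1.10 |
| 0.3 | 9.0% | 1.16 |
| 0.486 | 11.7% | 1.25 |
| 0.6 | 13.6% | 1.30 |

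- 5-level score: 8.1–14.0%.
- Two attacks each: 6.9–11.9% (10.0% at 0.486).
- At the 240 cap (240 × 0.68 = 163, about 82 per arm): 7.4–12.8%, so a larger trial does not help.
- With participant-clustered variance: 4.8–5.5% in all these scenarios.
- Check at ρ = 0: 5.2% unadjusted and 5.1% clustered, so the excess comes from the clustering.

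The simulation sits slightly below the formula because cutting a latent score into categories lowers its correlation. A latent 0.486 becomes about 0.42 on the score. There D = 1 + 0.42 × 8/6 = 1.56 and the formula gives 11.7%.

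**Robustness.** Category probabilities of 0.20/0.30/0.30/0.20 and 0.12/0.14/0.37/0.37 give 12.1% and 11.7% at latent 0.486. A likelihood-ratio test gives 6.9% at latent 0.15 and 13.6% at 0.56. A robust Wald test holds 5.3–5.4%.

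**Which endpoints are exposed.** AMSP2 and PF2 are cut-points of the HS2 score, and MBSF2 is a cut-point of MBS2. These binary tests come first and are adjusted. With identical score distributions in both arms at ρ = 0.486, AMSP2, PF2 and HS2 all reject in 1.4% of trials, and MBSF2 and MBS2 both reject in 3.2%. HS2 and MBS2 are thus largely protected. The other five ordinal endpoints have no such earlier test on the same score.

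**The case against.** The strongest reply is that the SAP does not plan to ignore clustering. Its text covers all hypothesis tests and says participants are clusters. The binary rows of Table 3 also say only Pearson's chi-square and take their adjustment from that same text. On this reading the defect is an unspecified method, and 7–14% is what happens only if the intention is not carried out. The point about intent stands. But the text supplies a usable adjustment for the binary rows and none for the ordinal row, so an analyst who follows the named methods arrives at the unadjusted test.

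The range also rests on assumed correlations, category probabilities and a latent-normal model. That stands too: only the omission is certain from the documents. Taking 0.486 as the correlation of the score itself, not of the latent variable, moves the formula result to 12.7%.

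A third reply is that the simulated rates are for a stand-alone test, while FDS2 is reached only after six rejections. At correlation 0.486, the rate given a genuine PF2 rejection is 10.6–11.4%, close to the stand-alone 11.7%. That settles the point for that gate only. The overall probability of a false labelling claim has not been computed.

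Finally, Protocol 16.7 makes AMSP2 the sole pass/fail criterion, so the consequence is limited to lower-order labelling claims. That is correct.

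**Conclusion.** The concern holds, as something that should be fixed. Seven of the twelve secondary tests have no valid clustered method, and the model named for them, fitted as written, exceeds its 5% level. The size is about 7–14% per test when reached, for within-participant correlations of 0.2 to 0.6 and either attack pattern. At the SAP's only value, 0.486, it is 11.7% by simulation and 12.7% by formula with the 1/2/3 mix, and 10.0% and 10.8% with two attacks each. The practical exposure is FDS2, PS48, LSS2, NS2 and SSS2, and through them Res24 and FR48. The primary endpoint and PF2 are not affected.

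**What to change.** In the categorical row of SAP Table 3, specify one method, for example: *proportional-odds (cumulative-logit) model with device type, fitted to all study attacks, with robust (GEE/sandwich) variance clustered on participant; two-sided Wald test*. A participant random effect, as already used in SAP 1.8, would also close the gap. What matters is that one method is named before these endpoints are analysed.

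The change is one table cell and standard software, with no change to design, data collection or sample size. SAP 1.7.3 commits the sponsor to submit SAP changes to the Competent Authorities for approval, so that step must be counted. The statistical price is standard errors about 10–25% larger for correlations of 0.2 to 0.486 in the simulation. The design-effect formula gives 13–28% (√1.267 = 1.13; √1.648 = 1.28). Claims on these endpoints become harder to win.

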# 1.8 Homogeneity Across Study Sites

The homogeneity of the treatment effect across study sites will be evaluated using a generalized linear mixed model where device used and site are fixed effects and each patient is a random effect (cluster). Homogeneity of the treatment effect between subjects in the United States and subjects outside the United States will also be evaluated using a generalized linear mixed model. If heterogeneity is detected, exploratory analyses will be conducted, which may include adjusting analyses for baseline characteristics that significantly differ across sites.

# 1.9 Sensitivity Analysis for Missing Data

All attempts will be made to minimize missing data and to ensure the primary endpoint is powered such that an analysis of complete data will be considered the primary analysis for the study.

A sensitivity analysis of the primary effectiveness endpoint will be conducted as a tipping-point analysis, to examine the impact of missing data. It will only be conducted if the hypothesis test passes (i.e., rejects H0). We will start by assuming that all missing primary effectiveness endpoints have values indicating the inferiority of Rehaler (i.e. all subjects missing data in the treatment group did not have AMSP2 and all subjects missing the primary endpoint in the control group did have AMSP2). If the primary effectiveness hypothesis is not passed, we will change one missing endpoint until the hypothesis test passes. This will enable determination of the amount of missing data that would alter the final result on the primary effectiveness endpoint.

If any study attacks in the ITT population have missing outcomes at 2 hours and: 1) the missingness is due to the patient's study condition or treatment (missing for cause) or 2) the analysis is underpowered using complete data (observed proportion of missingness is greater than assumed), five (5) multiple imputations will be used for the primary effectiveness endpoint. This consists of imputing values for each missing value as a set, analyzing the results for each set, and then pooling the results. The primary effectiveness endpoint is binary, so the imputation method will be a multiple logistic regression.

In addition, an analysis will be conducted in which if the hypothesis test of the primary effectiveness endpoint does not pass, the hypothesis test will be repeated using the per-protocol analysis population. This test is for sponsor's information only, and will not be used to support the study objective.

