16.9 Handling of Missing Data

All attempts will be made to minimize missing data. However, if any subjects in the ITT population have missing primary endpoints, five (5) multiple imputations will be used for the analyses. This consists of imputing values for each missing value as a set, analyzing the results for each set, and then pooling the results. The primary effectiveness endpoint is binary, so the imputation method will be a multiple logistic regression.

17 Data capture and management

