#### 1.7 Outcomes and Analysis

#### 1.7.1 Primary hypothesis

In line with earlier studies on aura-phase treatment (Bates D. et al., 1994; Olesen J. et al., 2004), the trial's **primary end point** will be absence of moderate or severe pain at 2 hours (AMSP2), ), i.e. the percentage of study attacks in which the participant reported absence of headache of moderate/severe intensity at 2 hours post-treatment initiation. "Study attacks" are all attacks treated and reported during Stage 1, apart from the first attack which is a training attack and is not included in the analysis.

The intention-to-treat (ITT) analysis set will be used for the primary effectiveness hypothesis test. The primary effectiveness hypothesis is:

 $H_0: p_{Rehaler} = p_{sham}$ 

 $H_a: p_{\text{Rehaler}} \neq p_{\text{sham}}$ 

Where:

pRehaler = proportion of attacks in the Rehaler group with AMSP2

psham = proportion of attacks in the sham group with AMSP2

The primary effectiveness hypothesis will be tested using a two-sided adjusted  $\chi^2$  test for clustered binary data (Donner and Banting, 1988) at a 5% level of significance.

If Pearson's chi-squared test statistic is written as  $\chi^2 = \sum_{i=1}^{G} \chi_i^2$  with G = the number of treatment groups, then the adjusted  $\chi^2$  approximately follows a chi-squared distribution with G-1 degrees of freedom and is calculated as follows (Donner and Banting, 1988):

$$\chi_A^2 = \sum_{i=1}^G \frac{\chi_i^2}{\overline{C_i}}$$

Where:

- $\overline{C}_{l} = \sum_{j=1}^{n_{i}} \frac{m_{ij}C_{ij}}{\sum m_{ij}}$
- $C_{ij} = 1 + (m_{ij} 1)\rho$
- G is the number of treatment groups
- ni is the number of individuals in group i
- ρ is the correlation coefficient between any two responses in the same individual
- mij denotes the number of observations for individual j in group i

The corresponding 95% confidence interval for the difference in proportion of attacks with AMSP2 between the Rehaler and sham groups will also be calculated as follows (Donner and Klar, 1993):

95% Confidence Interval:  $(\hat{p}_{Rehaler} - \hat{p}_{sham}) \pm 1.96 * \widehat{SE}(\hat{p}_{Rehaler} - \hat{p}_{sham})$ 

Where:

- $\hat{p}_{Rehaler}$  = observed proportion of attacks in the Rehaler group with AMSP2
- $\hat{p}_{sham}$  = observed proportion of attacks in the sham group with AMSP2

• 

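### The imputation of missing 2-hour outcomes specifies no patient term; run as a single-level logistic model, it would lower the ICC and modestly inflate the type I error of the adjusted chi-square

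*SAP*

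**What the plan says.** **Imputation model.** SAP 1.9: "The primary effectiveness endpoint is binary, so the imputation method will be a multiple logistic regression". Protocol 16.9 gives the same one-line method. Both call for five imputed sets, analysed separately and then pooled. Neither lists predictors, a patient effect or a pooling rule.

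**When it applies.** Protocol 16.9 is unconditional: "if any subjects in the ITT population have missing primary endpoints, five (5) multiple imputations will be used for the analyses". Protocol 16.8.1 also says that imputation will be done, and refers to the SAP for the method. SAP 1.6.1 makes imputation optional. SAP 1.9 treats the complete-data analysis as primary and imputes only on one of two triggers: outcomes missing because of the patient's condition or treatment, or more missingness than assumed, leaving the complete-data analysis underpowered.

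**Clustering.** SAP 1.7.3 treats the attack as the data point, and "each patient will constitute a cluster including from one to three data points". The primary test is the adjusted chi-square (SAP 1.7.1). It divides each arm's contribution by a variance inflation factor built from the within-patient correlation ρ, whose estimator is not named. SAP 1.8 specifies a patient random effect for the homogeneity model.

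**The concern.** The adjusted chi-square protects type I error only if ρ is estimated from data that keep the real within-patient correlation. A logistic imputation without patient information fills a missing attack from the arm-level rate, whatever the same patient reported in other attacks. The imputed values dilute the correlation, the estimated ρ falls, the variance inflation factor shrinks, and the test rejects too often under the null. Clustering is handled in the test and in the homogeneity model but is not carried into the imputation step. If imputation governs the final analysis, that would touch the primary p-value, and choosing the model after unblinding would be open to challenge.

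**Working it through.** **Inputs.**
- ICC, SAP 1.5.1: "The intraclass correlation coefficient (ICC) from preliminary data on this device was 0.486".
- Response rates, SAP 1.5.1: "For AMSP2, a 26% response rate in the sham group and a 61% response rate in the active group was assumed".
- Study attacks per patient: 1, 2 or 3, one third each (SAP 1.5.1).
- Losses: 22% of patients drop out and 10% of attacks lack 2-hour data (SAP 1.5.1).
- Threshold, SAP Table 3: "Threshold p value in full data set analysis: 0.048".

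**Step 1: reproduce the plan's figure.** The size-weighted mean number of attacks is (1 + 4 + 9)/(1 + 2 + 3) = 14/6 = 2.333. The design effect is 1 + (2.333 − 1) × 0.486 = 1.648. With 136 evaluable patients, 68 per arm × 2 attacks / 1.648 = 82.5 effective attacks per arm. Power for 61% against 26% at 0.048 is then 99.7% by formula and 99.5-99.7% by simulation. SAP Table 1 gives 99.1%, so the test and its inputs are understood correctly.

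**Step 2: effect on the ICC.** Let f be the fraction of attacks missing completely at random. After a single-level imputation, a pair of attacks in one patient is correlated only if both were observed, so the ICC becomes about 0.486 × (1 − f)². At f = 0.10 this is 0.486 × 0.81 = 0.394; at f = 0.20 it is 0.486 × 0.64 = 0.311.

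**Step 3: effect on the variance.** Relative to the variance of independent attacks with none missing:
- true variance of the pooled estimate: 1/(1 − f) + 0.648, where 0.648 = 1.333 × 0.486;
- variance credited by Rubin's rules: 1/(1 − f) + 0.648(1 − f)².

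At f = 0.10 the ratio is (1.111 + 0.525)/(1.111 + 0.648) = 0.930. The critical value for 0.048 is 1.977, and 1.977 × √0.930 = 1.907, which gives a two-sided error of 0.057.

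**Step 4: simulation under the null.** There were 40,000 trials per setting, with 78 patients per arm (200 × 0.78 / 2). The null rates were 0.26 and 0.435, the latter being the midpoint of 0.26 and 0.61. Correlation was beta-binomial, the imputation model was logistic with arm only, there were five imputations, and the ICC was re-estimated by ANOVA in each set. Pooling was by Rubin's rules or by the D2 rule, which combines the chi-square statistics. The Monte Carlo standard error is about √(0.05 × 0.95/40,000) = 0.001.

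| Attacks missing | Mean ICC after imputation | Variance ratio | Type I, formula | Type I, Rubin | Type I, D2 |
|---|---|---|---|---|---|
| 5% | 0.44 | 0.963 | 0.052 | 0.054 | 0.053 |
| 10% | 0.39 | 0.930 | 0.057 | 0.057-0.058 | 0.055-0.057 |
| 20% | 0.31 | 0.877 | 0.064 | 0.063-0.064 | 0.060 |
| 30% | 0.24 | 0.841 | 0.070 | 0.070 | 0.064-0.065 |

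The complete-data test on the same simulated trials gives 0.049-0.050.

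**Step 5: does a patient-aware model cure it?** Drawing missing attacks conditionally on the patient's observed attacks keeps the mean ICC at 0.481-0.485. Type I error is 0.050-0.052 (Rubin) or 0.048-0.051 (D2) across 5-30% missing.

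**The case against.** Three stronger readings are tempting, and the documents do not support them.

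1. *The SAP imputes with a model that ignores clustering.* It does not say so. It neither includes nor excludes a patient term, and it recognises clustering in SAP 1.7.3 and 1.8. The gap is an omission. The arm-only model above is an assumption, and the word multiple suggests more than one predictor. Covariates that predict a patient's response, such as the 1-hour headache score, would be expected to reduce the inflation; by how much was not computed.

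2. *The planned primary p-value will be inflated.* Under the SAP it is not, because complete data are primary. At the planned 10% missing, the second trigger is not met. Protocol section 16 presents itself as a summary and defers to the SAP for detail, which favours the SAP's rule. But the protocol's own text is unconditional, and neither document says which prevails. The second trigger also operates only above the assumed missingness, where the inflation is larger.

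3. *The direction follows from the text.* It does so only with an attack-level variance. The standard error printed in SAP 1.7.1 for the confidence interval divides by n, defined as individuals. With two attacks per patient on average, that variance is about twice too large. Pooled literally, it made the test conservative: type I error was about 0.009 at 10% missing and 0.015 at 20% (10,000 trials). The divisor may be a slip, but it shows that the result depends on a pooling procedure the plan leaves open.

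The simulated missingness is also completely at random. The SAP's first trigger concerns missingness related to condition or treatment, where bias could matter more; that was not modelled.

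All three limits stand. What remains is that a literal single-level reading of the stated method has a known defect, and nothing in either document rules that reading out.

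**Conclusion.** The point holds as an under-specified imputation model with a modest consequence. Run single-level with arm only, outcomes missing completely at random and an attack-level variance, it raises type I error by about 0.5 to 1 percentage point at the planned 10% missing (0.055-0.058 against 0.049-0.050). At 20% missing the error is 0.060-0.064. The primary p-value is exposed only if the protocol's rule governs or a SAP 1.9 trigger is met. The plan should be changed because the defect is avoidable at little cost and the two documents disagree on when imputation applies. It is not a reason to doubt the complete-data primary test.

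**What to change.** In SAP 1.9 and protocol 16.9:
- Impute with a logistic model that has a patient random intercept, or that includes the patient's other attack outcomes as predictors. Include arm and the time-0 and 1-hour headache scores, which the ePRO app already collects. Site is optional and is not needed to cure the ICC problem.
- Name the ICC estimator, say that it is recomputed in each imputed set, and name the pooling rule with an attack-level variance.
- Reconcile SAP 1.6.1 and 1.9 with protocol 16.8.1 and 16.9 on when imputation applies and which analysis is primary.

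The cost is wording in two documents, slightly more complex imputation code, and the submission to the authorities that SAP 1.7.3 requires for SAP changes. No new data are needed. The change should be settled before the final unblinding.
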